- 19 5) ALT level ≤ 2 ULN based on at least two determinations taken at least one month apart
20 during the 24 weeks before study entry with the second being at time of screening
- 21 6) Written informed consent

22

23 **Inclusion criteria: HBeAg negative group**

- 24
- 25 1) Age >18 years and older, male or female.
- 26 2) Known serum HBsAg positivity and HBeAg negativity at the time of screening.
- 27 3) Ongoing treatment with one or more NUCs for at least 192 weeks before study entry.
28 Subjects may have a brief interruption of treatment for medical reasons (e.g. breast feeding)
29 not to exceed 8 weeks and none within the 48 weeks before study entry.
- 30 4) HBV DNA levels <100 IU/mL, measured at least 12 months prior to, and upon enrollment to
31 the study
- 32 5) ALT level ≤ 2 ULN based on at least two determinations taken at least one month apart
33 during the 24 weeks before study entry with the second being at time of screening
- 34 6) Written informed consent

35

1 Exclusion criteria (for both eAg positive and negative patients)

- 2
- 3 1) Co-infection with HDV as defined by the presence of anti-HDV in serum and/or HDV antigen
- 4 in the liver.
- 5 2) Co-infection with HCV as defined by the presence of HCV RNA in serum.
- 6 3) Co-infection with HIV as defined by the presence of anti-HIV in serum.
- 7 4) Decompensated liver disease as defined by serum bilirubin >2.5 mg/dL (with direct bilirubin
- 8 > 0.5 mg/dL), prothrombin time of greater than 2 seconds prolonged, a serum albumin of
- 9 less than 3 g/dL, or a history of ascites, variceal bleeding or hepatic encephalopathy.
- 10 5) Presence of other causes of liver disease, (i.e. hemochromatosis, Wilson disease, alcoholic
- 11 liver disease, severe nonalcoholic steatohepatitis defined as the presence of marked
- 12 ballooning injury on liver biopsy, alpha-1-anti-trypsin deficiency).
- 13 6) A history of organ transplantation or in the absence of organ transplantation, any
- 14 immunosuppressive therapy requiring the use of more than 5 mg of prednisone (or its
- 15 equivalent) daily.
- 16 7) Significant systemic illness other than liver diseases including congestive heart failure, renal
- 17 failure, chronic pancreatitis and diabetes mellitus with poor control, that in the opinion of
- 18 the investigator may interfere with therapy.
- 19 8) Pregnancy or inability to practice contraception in patients capable of bearing or fathering
- 20 children
- 21 9) Lactating women.

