- 22 (4) Fatigue questionnaire (Promise 7)
- 23 (5) Visual analogue scale
- 24 (6) Routine blood panel: Chemistry 20 (sodium, chloride, potassium, bicarbonate, calcium,
 25 phosphate, magnesium, glucose, blood urine nitrogen, creatinine, uric acid, ALT, AST,
 26 LDH, CPK, Alkaline Phosphatase, total and direct bilirubin, albumin, total protein), CBC
 27 (hematocrit, hemoglobin, white blood cell count and differential, platelet count).
 28 Testing will also be done for anti-HAV, HBsAg, anti-HBs, HBeAg, anti-HBe, anti-HBc,
 29 anti-HCV, and stored sample for IL-28b testing. Baseline HBV DNA level by quantitative
 30 PCR (COBAS Ampliprep/COBAS Taqman HBV v2.0 Test: Roche Diagnostics, lower limit
 31 of quantification 116 copies /ml or 20 IU/ml, lower limit of detection 6 IU/ml)
- 32 (7) Extended blood panel: alpha fetoprotein, gGT, immunoglobulins, rheumatoid factor,
 33 ANUCs, SMA, lipid panel, thyroid panel, INR, reticulocyte count, ESR.
 34

- 1 (8) Research blood- one 10 ml serum and one 10 ml plasma tube stored frozen in 0.5-1.0
2 mL aliquots). The stored serum and plasma will be used to measure selected cytokines,
3 interferon-stimulated gene products [including IP10], quantitative HBsAg level (by
4 using the Roche Elecsys HBsAg automated quant assay) and for future research.
- 5 (9) Fifty milliliters of whole blood (green top tubes) for baseline immunological studies: NK
6 cell responses, CD4+ and CD8+ T cell HBV specific responses (peripheral blood
7 mononuclear cell [PBMC] studies)
- 8 (10) Urine tests: routine urinalysis and a pregnancy test for females of childbearing
9 potential
- 10 (11) Transient elastography
- 11

12 **Admission for pretreatment liver biopsy**

13

14 Once patients are deemed eligible to participate in the study based on results of the screening
15 labs, they will have 12 weeks to complete the liver biopsy and to begin add-on therapy with
16 peginterferon. Eligible patients will be admitted to 5NW to undergo a percutaneous liver biopsy.
17 The initial liver biopsy will be mostly for research purposes to measuring baseline levels of ISG
18 expression, pregenomic and cccDNA concentration and frequency and activity of liver infiltrating
19 HBV-specific NK cells but will also be used for the purpose of grading and staging of liver disease
20 before treatment and will provide useful information to the clinician and patient on whether the
21 liver disease is improving on current therapy. Grading and staging of the liver biopsy will

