22 performed by an expert hepatopathologist blinded to the clinical information using the modified
23 Ishak scoring system. This includes the histological activity index (HAI) for inflammation and
24 necrosis (scores ranging from 0 to 18). Fibrosis will be staged using the Ishak scoring system (0-
25 6, 0=no fibrosis, 6=cirrhosis). Slides will also be immunostained for HBsAg, HbcAg, and HDV
26 antigen by peroxidase-antiperoxidase techniques and scored as 0, 1, 2 or 3+ based upon the
27 percent of cells reactive for each viral antigen (0=none, 1=10%, 2=11% to 50% and 3= \geq 51% of
28 hepatocytes).

29 Liver-infiltrating lymphocytes will be assessed for frequency and function of NK cells. m-RNA
30 levels of ISG's, immune cell markers and chemokines/cytokines will be quantitated by real-time
31 PCR or nanostring. Intrahepatic pregenomic and cccDNA will also be quantitated by Southern
32 blotting or real-time PCR.

33
34 The following will be obtained on admission:

- 35 1) Brief clinical evaluation
- 36 2) Review patient's eligibility for study

- 1 3) Symptom questionnaire
- 2 4) Visual analogue scale
- 3 5) Fatigue questionnaire (Promise 7)
- 4 6) Abdominal ultrasound, CXR and 12 lead ECG (if not done within previous 6 months)
- 5 7) Chemistry 20 (sodium, chloride, potassium, bicarbonate, calcium, phosphate, magnesium,
- 6 glucose, blood urine nitrogen, creatinine, uric acid, ALT, AST, LDH, CPK, Alkaline
- 7 Phosphatase, total and direct bilirubin, albumin, total protein), CBC (hematocrit, hemoglobin,
- 8 white blood cell count and differential, platelet count).
- 9 8) HBV DNA viral load, qualitative and quantitative HBeAg and HBsAg measurement
- 10 9) 50 mL of blood in heparinized green top tubes for NK and T cell analysis.
- 11 10) Blood sample for storage (5 mL of blood separated into serum and stored frozen in 0.5-1.0
- 12 mL aliquots)
- 13 11) Liver biopsy cut into four sections, one (at least 1.5 cm) placed in formalin for routine light
- 14 microscopy and the other 3 (.3cm, .5cm and 1 cm) placed in RNA later and flash frozen in
- 15 liquid nitrogen 24 hours later for RNA and protein analyses and flow cytometry. A liver
- 16 biopsy fragment of > 5 mm will be used to assess the frequency and function of NK cells.
- 17 12) Discharge from hospital

18

19

20 **Initiation of Treatment**

21

22 Patients will be stratified on the basis of HBeAg status into 2 groups of 30 patients each, to receive

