13 c) **Any clinical adverse event, laboratory abnormality, or intercurrent illness**, which in the
14 opinion of the investigator indicates that continued participation in the study is not in the
15 best interest of the subject. If any of the following laboratory or clinical criteria is obtained
16 for any subject, the result must be repeated/confirmed within 72 hours. If the results are
17 confirmed, the subject must discontinue treatment. Clinical criteria must have Principal
18 Investigator or Sub-Investigator assessment prior to permanent discontinuation.
- 19 – Evidence of confirmed hepatic decompensation (Child-Pugh Class B or C, Score > 6)
20 (discontinue all treatment);
 - 21 – Platelets < 25 x 10⁹ cells/L;
 - 22 – Hemoglobin <8.5 g/dL
 - 23 – Absolute neutrophil count < 250 mm³/ml
 - 24 – Severe neuropsychiatric signs and symptoms (including depression) for both new and
25 worsening events that are considered clinically significant by the investigator.
26
- 27 d) **Pregnancy** women of childbearing potential must contact the investigator or study staff
28 immediately if they suspect they might be pregnant (eg, missed or late menstrual period) at
29 any time during study participation. If subjects become pregnant the research staff will stop
30 peginterferon, but subjects may continue taking their antiviral oral agent at the discretion of
31 the study doctor. The investigator will discuss possible management options with the
32 subject. Subjects who do become pregnant will continue to be followed for the outcome of
33 the pregnancy. The NIH will not cover any aspects of obstetrical, child or related care.
34

- 1 e) **Loss of ability to freely provide consent** through imprisonment or involuntary
 2 incarceration for treatment of either a psychiatric or physical (eg, infectious disease) illness.

3

4

5 **Stopping NUCs therapy**

6

7 Treatment with NUCs will be stopped under the following conditions

- 8 a) HBeAg loss, with or without anti HBe seroconversion, in eAg positive patients, that is
 9 confirmed on 2 separate tests, at least 6 months apart.
 10 b) HBsAg loss, with or without anti HBs seroconversion, that is confirmed in 2 separate tests, at
 11 least 6 months apart.

12

13

14

15 **Peginterferon Dose Modifications**

16

17 Dose modification of peginterferon α -2a should be managed according to Table 2. This table is based
 18 on recommendations from the peginterferon α -2a package insert, and have been modified as

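### Exclusion 4 sets no Child-Pugh limit although a confirmed score above 6 requires stopping, so under the usual scoring bands a borderline patient can enter already at the stopping score

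*Combined protocol and SAP*

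**What the plan says.** **Entry.** In the exclusion criteria, item 4 reads "Decompensated liver disease as defined by serum bilirubin >2.5 mg/dL (with direct bilirubin" above 0.5 mg/dL). It then lists, as alternatives, a prothrombin time prolonged by more than 2 seconds, albumin below 3 g/dL, or a history of ascites, variceal bleeding or encephalopathy. No inclusion or exclusion criterion uses a Child-Pugh score.

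**On treatment.** Under Stopping peginterferon therapy, item c, the first listed criterion is "Evidence of confirmed hepatic decompensation (Child-Pugh Class B or C, Score > 6"). The text leading into the list says that "for any subject, the result must be repeated/confirmed within 72 hours. If the results are" confirmed, treatment must stop. It also asks, for clinical criteria, for Principal "Investigator or Sub-Investigator assessment prior to permanent discontinuation". There is no change-from-baseline condition, and no Child-Pugh point bands are printed anywhere.

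**Between the two.** INR is in the screening panel ("lipid panel, thyroid panel, INR, reticulocyte count, ESR"), and no other INR is scheduled before treatment. Both the biopsy admission and Day 0 list the item "Review patient's eligibility for study", and both draw chemistry that includes "Phosphatase, total and direct bilirubin, albumin, total protein), CBC (hematocrit, hemoglobin". On Day 0, chemistry is item 6 and the first injection is item 11. Of the first biopsy the protocol says "The initial liver biopsy will be mostly for research purposes to measuring baseline levels of ISG" expression, although it is also used to grade and stage the liver disease.

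**The concern.** Entry uses single-marker limits and stopping uses a composite score. A patient can sit just inside two of the single limits, pass exclusion 4, and have a composite score that the stopping rule calls decompensation. Because the rule takes no account of the baseline score, a stable patient of this kind would meet it without any deterioration.

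Such a patient could undergo two liver biopsies, done mainly for research, and receive a first peginterferon injection while already at the protocol's own stopping score. Cirrhosis is not an exclusion (cirrhosis status is a listed baseline characteristic), so borderline hepatic reserve is possible in this population. The issue is one of safety and internal consistency, not of inference.

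**Working it through.** The plan gives no derived figure to reproduce here; the check scores patients who pass exclusion 4.

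**Inputs from the protocol.** With direct bilirubin above 0.5 mg/dL, an eligible patient has total bilirubin of at most 2.5 mg/dL, albumin of at least 3.0 g/dL, prothrombin time prolonged by at most 2 s, and no history of ascites or encephalopathy. The stopping score is above 6.

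**Inputs assumed.** Non-cholestatic bands: bilirubin below 2 / 2 to 3 / above 3 mg/dL score 1 / 2 / 3; albumin above 3.5 / 2.8 to 3.5 / below 2.8 g/dL score 1 / 2 / 3; prothrombin time prolonged by less than 4 s, no ascites and no encephalopathy score 1 each. The alternative is cholestatic bands, with 1 point for bilirubin below 4 mg/dL.

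**Coagulation stays at 1 point if INR is used instead.** Taking a normal time of 10 to 14 s and a sensitivity index (ISI) of 1.0 to 2.0, both assumed, 2 s of prolongation gives an INR between (16/14)^1.0 = 1.14 and (12/10)^2.0 = 1.44. Both are below an assumed 1-point limit of 1.7.

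**Score** = bilirubin + albumin + coagulation + ascites + encephalopathy.

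- Bilirubin 2.0 to 2.5 and albumin 3.0 to 3.5: 2 + 2 + 1 + 1 + 1 = 7, above 6.
- Bilirubin 2.5 with normal albumin: 2 + 1 + 1 + 1 + 1 = 6, not above 6.
- Albumin 3.0 with normal bilirubin: 1 + 2 + 1 + 1 + 1 = 6, not above 6.

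Both markers must therefore be borderline at once.

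**Range over the bands.** On a grid in steps of 0.1 with direct bilirubin above 0.5, the eligible cells are 20 bilirubin values (0.6 to 2.5) × 21 albumin values (3.0 to 5.0) = 420.

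| Bands assumed | Highest eligible score | Cells scoring above 6 |
|---|---|---|
| Non-cholestatic, band limits inclusive | 7 | 6 × 6 = 36 |
| Non-cholestatic, band limits strict | 7 | 5 × 5 = 25 |
| Cholestatic | 6 | 0 |

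Moving the lower edge of the 2-point albumin band from 2.8 to 3.0 changes nothing. The cells show where the conflict lies; they are not patient frequencies, and the documents give none.

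**Direct bilirubin of 0.5 mg/dL or less.** Exclusion 4 then sets no limit on total bilirubin. Total 3.2, direct 0.4, albumin 4.0 is eligible and scores 3 + 1 + 1 + 1 + 1 = 7 under non-cholestatic bands. With albumin 3.0 to 3.5 it is 3 + 2 + 1 + 1 + 1 = 8. If bilirubin were given 1 point at entry only, the first patient would enter at 5 and still stand at 7 under the stopping rule. With 1 point in both places the totals are 5 and 6 at entry and at stopping alike.

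**Exposure.** The second weekly injection is due 7 × 24 = 168 h after the first. If Day 0 chemistry is scored after the injection, confirmation within 72 h comes before it, so one dose is at issue. If it is scored before the injection, none is. If the first chemistry scored is at week 2, injections on days 0, 7 and possibly 14 would already have been given.

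**The case against.** The strongest reply is that the conflict is not in the text alone. The protocol prints no bands, and one plausible set gives no conflict when direct bilirubin exceeds 0.5 mg/dL. Entry and stopping rules also serve different purposes, and a stopping rule stricter than the entry rule errs on the safe side. All of this stands, and it limits the point to a conditional one. A required stop tied to a score whose bands are not named is still worth completing.

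A reader might infer that an affected patient would be stopped automatically after one dose. The documents do not support that. The criterion sits in an item framed around the investigator's judgement of the subject's best interest, and clinical criteria need investigator assessment. Table 1 schedules INR only at screening and at post-treatment week 48, so the full score cannot be calculated from scheduled on-treatment tests. The stop is probably triggered clinically.

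A reader might also infer that the score is not calculated before dosing. The protocol says only that eligibility is reviewed. What is shown is that no instruction to calculate it exists, not that no investigator would.

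Other discretion does not clearly close the gap. Exclusion 7 is limited to illness other than liver disease, and exclusion 19 concerns whether the patient can be followed for a year.

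Finally, few patients are likely to be affected, given at least 192 weeks of nucleos(t)ide treatment, HBV DNA below 100 IU/mL and ALT at most 2 × ULN. That is a fair argument for low severity.

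**Conclusion.** The point holds in a limited form. The two definitions differ on the face of the text, and no entry limit on the Child-Pugh score links them. Under non-cholestatic bands an eligible patient with direct bilirubin above 0.5 mg/dL can start at 7; under cholestatic bands the maximum for such a patient is 6. Patients with direct bilirubin of 0.5 mg/dL or less can total 7 or 8 under non-cholestatic bands, so an entry limit that scores their bilirubin differently from the stopping rule would leave part of the conflict in place.

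The gain from correction is small: up to two biopsies and about one dose (if Day 0 chemistry is scored), in a number of patients that the documents do not allow one to estimate but that is probably few. A reader should not infer any effect on power or on the analysis. Severity is low; the case for acting is that the change is cheap.

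**What to change.** - Add a Child-Pugh score above 6 to exclusion 4 as a further alternative.
- Name the Child-Pugh bands that apply, including how values on a band limit are scored.
- Use the same convention at entry and in the stopping criterion, including for direct bilirubin of 0.5 mg/dL or less. For example, score bilirubin as 1 point in both places for isolated indirect hyperbilirubinemia. With one convention, every eligible patient starts at 6 or below under any bands.
- Calculate the score at screening from bilirubin, albumin, INR and examination, which can spare both biopsies. Recheck bilirubin and albumin at the existing Day 0 eligibility review before the injection, since patients have 12 weeks from being found eligible to complete the biopsy and start treatment. This can still spare the second biopsy and the dose. Carry the screening INR forward.

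The cost is a wording amendment in two places and a calculated field on the eligibility form, with no new test. Day 0 chemistry must be read before dosing. At most a few borderline candidates are lost: with direct bilirubin above 0.5 mg/dL, those with bilirubin 2.0 to 2.5 mg/dL and albumin 3.0 to 3.5 g/dL under non-cholestatic bands. The stopping threshold stays at a score above 6.

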- 22 10) Hepatocellular carcinoma (HCC), or the presence of a mass on imaging studies of the liver
- 23 that is suggestive of HCC, or an alpha-fetoprotein level of greater than 500 ng/mL.
- 24 11) eGFR < 50 ml/min, serum creatinine > 1.3 mg/dl or urine protein >1 gram/24-hours
- 25 12) History of hypersensitivity to pegylated interferon-alpha
- 26 13) Platelet count <70 mm³/dL
- 27 14) Hgb <12 g/dL for males and <11 g/dL for females
- 28 15) Active ethanol/drug abuse/psychiatric problems such as major depression, schizophrenia,
- 29 bipolar illness, obsessive-compulsive disorder, severe anxiety, or personality disorder that,
- 30 in the investigator's opinion, might interfere with participation in the study.
- 31 16) History of malignancy or treatment for a malignancy within the past 3 years (except
- 32 adequately treated carcinoma in situ or basal cell carcinoma of the skin).
- 33 17) Any medical condition requiring, or likely to require, chronic systemic administration of
- 34 corticosteroids or other immunosuppressive medications during the course of this study.
- 35 18) History of immune-mediated disease, or cerebrovascular, chronic pulmonary or cardiac
- 36 disease associated with functional limitation, retinopathy, uncontrolled thyroid disease,

- 1 poorly controlled diabetes or uncontrolled seizure disorder, as determined by a study
 2 physician.
- 3 19) Presence of conditions that, in the opinion of the investigators, would not allow the patient
 4 to be followed in the current study for at 1 year.
- 5 20) For subjects who interrupt therapy, documentation of a viral load >1,000 IU/ml while off
 6 therapy.
 7

8 **STUDY DESIGN AND PROCEDURES**

9

10 **Screening**

11 Eligible patients will be seen in the outpatient liver clinic of the NIH Clinical Center. At the screening
 12 visit, potential benefits and risks associated with the study will be explained to the study participants
 13 by an investigator in laymen's language. Written informed consent will be obtained and documented
 14 in the participant's chart. Whenever possible, the informed consent form will be provided to the
 15 potential participants in advance. Only the principal and associate investigators from the Liver
 16 Disease Branch, NIDDK, will be eligible to obtain consent for this study.
 17

18 The following screening procedures will be performed:

- 19 (1) Obtain signed informed consent
- 20 (2) History and physical examination
- 21 (3) Symptom questionnaire

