8 Patients will undergo up to two liver biopsies in this protocol: one before therapy and a second six
9 hours after the initial injection of peginterferon alfa-2a. Patients with inadequate platelet counts
10 ($<70,000/\text{mm}^3$) or coagulation parameters (prothrombin time > 15 seconds, INR >1.7) will undergo
11 transjugular liver biopsy after correction of the laboratory abnormalities as a part of this protocol.
12 Patients requiring liver biopsy will be admitted to the Clinical Center for two days for this procedure
13 and other blood testing. The major side effects of liver biopsy are pain, bacteremia, puncture of
14 another organ and bleeding. Local pain and discomfort at the liver biopsy site occurs in about 20% of
15 persons undergoing percutaneous liver biopsy. This is transient (lasting one to twelve hours) and is
16 usually mild, rarely requiring analgesics. Bacteremia occurs in 1-2% of persons undergoing liver
17 biopsy. In the absence of bile duct obstruction, this is almost always self-limited and is rarely
18 symptomatic. Significant bleeding after liver biopsy is the most serious side effect of this procedure.
19 In the absence of a blood coagulation defect or hepatic malignancy, significant bleeding is rare,
20 occurring in less than one in a thousand cases of liver biopsy. Death due to bleeding after liver
21 biopsy has been reported in less than 1/10,000 cases. At the NIH Clinical Center, the Liver Diseases
22 Branch has performed approximately 150 liver biopsies each year for the last 20 years. During this
23 time, only two patients died as a complication of biopsy. One of these patients had cirrhosis and
24 advanced hepatocellular carcinoma and the second had severe coagulation disorders. Both bled from
25 the liver biopsy site and died after surgical attempts to stop the bleeding were unsuccessful.

27 **The risks and hazards of Peginterferon therapy**

28 Local pain and erythema at the site of subcutaneous injection. This is usually mild and is no greater
29 than the pain and irritation associated with other subcutaneous injections. Severe local reactions
30 have been described but are rare
31 A syndrome of fever, malaise, headaches and muscle aches. These influenza- like symptoms occur
32 typically after the first injection and decrease in severity with subsequent treatments. Fever can be as
33 high as 40°C. The fatigue often persists or reappears with prolonged therapy with interferon and is

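### Two safety thresholds, the platelet exclusion limit and the neutrophil stopping limit, are printed in units that cannot express a cell count

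*Combined protocol and SAP*

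**What the plan says.** The list of exclusion criteria, item 13, reads "Platelet count <70 mm³/dL". Under Stopping peginterferon therapy, item c, one of the laboratory criteria that requires discontinuation once confirmed on repeat is "Absolute neutrophil count < 250 mm³/ml".

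Other places give the same two quantities in valid units:

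- In the same stopping list, the platelet limit is 25 x 10^9 cells/L.
- Table 2 gives its platelet bands (cut at 50 and 25) and neutrophil bands (cut at 0.75 and 0.25) in 10^9 cells/L, and the neutrophil restart level as 1000/mm3.
- Under Hazards and Discomforts, the section on percutaneous liver biopsy defines "Patients with inadequate platelet counts" as below 70,000/mm3. It sends those patients to "transjugular liver biopsy after correction of the laboratory abnormalities as a part of this protocol".

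The section on admission for the pretreatment biopsy bases eligibility on the screening laboratory results and then allows 12 weeks to biopsy and start of peginterferon. The biopsy admission and day 0 each include a review of "eligibility for study" and a blood count with "white blood cell count and differential, platelet count".

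**The concern.** A platelet or neutrophil limit has to be a number of cells per volume of blood. Cubic millimetres, decilitres and millilitres are all volumes, so both printed limits reduce to pure ratios. No laboratory report can be set against them.

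What is at stake is the use of two rules that act directly on patients. Criterion 13 decides who may enter a trial that requires two liver biopsies and a drug that lowers platelets. The neutrophil line is a mandatory discontinuation threshold. Staff apply such lines as they stand in the eligibility list or the stopping rules, and should not have to reconstruct them from a risk description or a dosing table.

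**Working it through.** **Inputs.** Criterion 13: 70 mm3/dL. Neutrophil stopping rule: 250 mm3/ml. Biopsy risk section: platelets 70,000/mm3. Stopping rules: platelets 25 x 10^9/L. Table 2: full peginterferon dose kept at platelets of 50 x 10^9/L or more; lowest neutrophil band below 0.25 x 10^9/L. Conversions: 1 dL = 100,000 mm3; 1 ml = 1,000 mm3; 1 L = 10^6 mm3.

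**Step 1: what the printed units mean.**

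- Platelets: 70 mm3/dL = 70 / 100,000 = 0.0007, with no dimension.
- Neutrophils: 250 mm3/ml = 250 / 1,000 = 0.25, with no dimension. That this numeral matches Table 2's 0.25 is a coincidence of the conversion; it is not a count in 10^9/L.

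**Step 2: which platelet count is meant.**

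| Reading of criterion 13 | In 10^9/L | Against the stopping level of 25 x 10^9/L |
|---|---|---|
| 70 per mm3 | 70 x 10^6 / 10^9 = 0.07 | 25 / 0.07 = about 357 times lower |
| 70 per dL | 70 / 100,000 = 0.0007 per mm3, or 0.0000007 | lower still |
| 70,000 per mm3 | 70,000 x 10^6 / 10^9 = 70 | 70 / 25 = 2.8 times higher |

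An entry limit far below the level at which treatment must stop makes no sense. The third reading equals the cut-off in the biopsy risk section and is 70 / 50 = 1.4 times the lowest count at which Table 2 keeps the full dose. It is the only reading of the three that fits the rest of the protocol.

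**Step 3: which neutrophil count is meant.** 250/mm3 x 10^6 mm3/L = 0.25 x 10^9/L, exactly the upper edge of Table 2's lowest neutrophil band.

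**Step 4: is this a fault of text extraction?** Probably not. The same construction occurs in two separate sections with two different denominators, while the platelet line in the same stopping list is correct.

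**The case against.** The strongest reply is that this is proofreading. Only one value is sensible in each case, both can be found elsewhere in the protocol, and screening is done at one clinic by one group of investigators. No patient can be shown to have been misclassified. All of this stands, and it is why the point is minor. It does not make the lines usable as printed, and the correction costs almost nothing.

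A reader might go further and infer that criterion 13 contradicts the biopsy risk section, since one excludes patients below 70,000/mm3 and the other gives them a transjugular biopsy within the protocol. The documents do not support that. Eligibility is set on screening results, and patients then "labs, they will have 12 weeks to complete the liver biopsy and to begin add-on therapy with" peginterferon, so a count can fall after screening. Criterion 13 carries no time limit, and eligibility is reviewed with a blood count at the biopsy admission and on day 0, so excluding such a patient is a natural reading. The transjugular wording sits in a description of risk. Which provision governs a later fall is unstated, but nothing directs an uncorrected percutaneous biopsy.

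A reader might also want to settle that question by limiting criterion 13 to the screening visit. That would not be a neutral edit, because it would narrow a safety exclusion. Take, for illustration, a patient with 60 x 10^9/L at the biopsy admission. That patient could go on to a research biopsy and to peginterferon, for which the hazards section gives a platelet fall of 13 to 52%. This leads to 60 x 0.87 = 52.2 down to 60 x 0.48 = 28.8 x 10^9/L. Most of that range is below Table 2's dose-reduction level of 50, and the low end is close to the stopping level of 25. Nothing in the documents favours that choice over exclusion.

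**Conclusion.** Both thresholds are wrong as printed. The intended values are platelets below 70,000/mm3 (70 x 10^9/L) and neutrophils below 250/mm3 (0.25 x 10^9/L). These are inferences, but well-supported ones: each matches a figure printed in valid units elsewhere in the protocol, and the platelet value also fits the scale of the dosing and stopping levels. The conclusion assumes that the printed units are the protocol's own and not an artefact of reading the PDF.

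Severity is minor, with no effect on sample size, power or analysis. The documents do not say how often counts fall below 70,000/mm3 after screening, so no number of affected patients can be given. How the transjugular provision fits with the repeat eligibility reviews is something for the sponsor to clarify, not an error.

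**What to change.** Make two text corrections:

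- Exclusion criterion 13: *Platelet count <70,000/mm3 (70 x 10^9/L)*.
- Stopping peginterferon therapy, item c: *Absolute neutrophil count <250/mm3 (0.25 x 10^9/L)*.

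Do not add a screening-only limit to criterion 13, and leave the biopsy risk section as it is. If the sponsor wishes to say whether a count that falls below 70,000/mm3 after screening leads to exclusion or to the transjugular route, one sentence would do. That is a separate safety decision. The cost of the two corrections is a short wording amendment; no procedure, design feature or analysis changes.
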